5. Lack of appetite, nausea, vomiting
6. Dyspnea
7. Headache, pain in the chest, bone pain
8. Priapism
9. Increase/decrease blood pressure
10. Anaphylactic reactions/erythema

Risks for blood draw:

- Occurrence of discomfort and/or a bruise at the site of puncture
- Less commonly, fainting
- The formation of a clot or swelling in the vein and surrounding tissue
- Bleeding from the puncture site
- On rare occasions an infection may develop at the site where the blood is collected

Potential Risks of No Treatment

Since Omegaven® will only be offered to those patients for whom no standard therapy has been safe and effective, the risks of not being treated are those allowing for the natural history of their disease and associated clinical manifestations to progress. These include fulminate liver failure and death.

VII. Overall Risk Assessment

Patients will be at some risk inherent in taking a pharmaceutical agent that has not been fully evaluated for long duration treatment. However, the availability of safety data demonstrates no life-threatening risks or toxicities to vital organs or physiologic functions. The potential benefits of Omegaven® in this patient population are mainly based on human trials and our own experience.

VIII. Risk Category

The research involves greater than minimal risk, but presents the prospect of direct benefit to the individual subjects.

IX. Methods

A. Subject Selection

No concomitant medications will prohibit enrollment.

Inclusion Criteria

1. Males and females ages one month of age to 18 years of age
2. Patients with intestinal failure on TPN
3. Patients who have a conjugated or direct bilirubin of ≥ 3 mg/dl for more than 4 weeks and in whom other causes of cholestasis have been excluded with reasonable certainty utilizing biochemical, serologic, microbiologic, and radiographic techniques. Liver biopsy is not required to rule out other disorders, but may be utilized at the clinician's discretion
4. Patients in whom reduction of IV soy-based lipid load to an **average** <1.2 g/kg body weight/day has failed to reduce the conjugated or direct bilirubin within ≥ 30 days of implementation

5. Willing to use birth control during study participation for females of child-bearing potential, as determined by investigator.
6. Signed informed consent for use of Omegaven® obtained

Exclusion Criteria

1. Any of the contraindications to use of Omegaven®

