The primary endpoint will be reduction in conjugated or direct bilirubin level to below 1 mg/dl. Data from previous retrospective analyses and prospective uncontrolled studies suggest that from the inception of Omegaven® therapy, conjugated or direct bilirubin will remain elevated for approximately 8 weeks at levels comparable to those observed prior to administration of Omegaven®. Subsequently, levels are expected to fall by approximately 1 mg/dl/week until they normalize. The time to normalization will vary according to each patient's baseline conjugated or direct bilirubin level. Thus, a patient who begins Omegaven® with a conjugated or direct bilirubin level of 7 mg/dl is likely to experience normalization within 14 weeks (8+6 weeks). We will compare the group receiving Omegaven® with historical controls from our internal registry who have demonstrated cholestasis while on Intralipid®. We will compare changes in conjugated/direct bilirubin concentration over time between groups via Kaplan-Meier analysis (see Statistics section XIII).

Secondary endpoints will be: normalization of total bilirubin and liver enzymes. Differences in these values at the end of 14 weeks of therapy will be compared with those of controls via Kaplan-Meier analysis identical to that employed for conjugated and direct bilirubin levels. Furthermore, we expect that elevated triglyceride levels which might be present at the initiation of therapy will have normalized at the same time that liver profiles have normalized.

XI. Assessment of Safety/Data Safety Monitoring Board

A DSMB will monitor the study for the occurrence of adverse events (both serious and otherwise). A significant increase in the rate of adverse events would be cause for concern for the safety of participants in the study. Information on adverse events will be presented in several ways: (1) listings of serious adverse events with accompanying narrative summary by the PI; (2) summaries of adverse events by body system and type of event. This information will be presented to the DSMB.

The DSMB will also monitor the efficacy and the conduct of the study. Interim monitoring reports for the DSMB will include, but will not be limited to, such tabulations as:

1. platelet counts
2. essential fatty acid profiles
3. coagulation studies
4. liver profiles

5. renal profiles

The DSMB will meet at least once per year and possibly more frequently given the expected speed of recruitment and study medication administration.

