All adverse events will be followed until they are resolved or the patient's participation in the treatment ends (i.e., until a final report is completed for that patient).

In addition, all SAEs and those non serious events assessed by the Investigator as attributable (i.e. possibly, probably, definitely related to the drug) will continue to be followed even after the patient's participation in the treatment is over. Such events will be followed until they resolve or until the Investigator assesses them as "chronic" or "stable." Resolution of such events is to be documented in the CRF.

XIII. Statistics

We selected a study number of 25 patients (5 patients a year for 5 years) even though, statistically, a number of 19 will be satisfactory based upon power analysis. We know from our current registry that 10% of historic controls will experience resolution of cholestasis within 8 weeks while receiving Intralipid®, and we know from the data of Gura, et al (5) that approximately 50% of experimental subjects will experience resolution of cholestasis within eight weeks while receiving Omegaven®. Thus, achieving an alpha of 0.05 and a beta of 0.80, a sample size of 19 patients and 19 controls will be adequate (11). However, insofar as this is a compassionate release protocol, we will not refuse entry into the study even if we have shown statistically that Omegaven® is efficacious. We estimate that at most we will acquire five patients per year, and we anticipate that within five years, Omegaven® or SMOF (soy, MCT, olive oil and fish oil) parenteral lipids will have obtained FDA approval for clinical use.

The analysis populations will include (1) subjects receiving Omegaven® under this protocol and (2) historical controls from our internal registry who have demonstrated cholestasis while on Intralipid®. Paired t-tests will be used to report the statistical significance of differences between means. A p value of 0.05 or less will be considered significant. Wilcoxon Tests will be used to report the statistical significant differences between medians, and χ^2 tests/Fisher's exact tests will be used to report proportions. A Kaplan-Meier analysis will compare changes in conjugated/direct bilirubin concentration over time between groups. Cox proportional hazard models will be used to estimate crude and adjusted hazard ratios. Analyses will be performed via SAS 9.2 (SAS Institute Inc, Cary, NC) and S-Plus 8.1.1 (Insightful, Inc, Seattle, WA).

IX. Data Management

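### Under the delayed response that section X predicts, the single Cox hazard ratio planned in section XIII depends heavily on a follow-up cut-off that the plan never fixes

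*Combined protocol and SAP*

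**What the plan says.** The event is defined in section X (Assessment of Efficacy): "The primary endpoint will be reduction in conjugated or direct bilirubin level to below 1 mg/dl". No assessment time is attached to it.

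The same section predicts the course on treatment. It says "conjugated or direct bilirubin will remain elevated for approximately 8 weeks at levels comparable to those observed prior to administration", after which "levels are expected to fall by approximately 1 mg/dl/week until they normalize". Its worked example is a patient starting at 7 mg/dl, who "is likely to experience normalization within 14 weeks (8+6 weeks").

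Section XIII (Statistics) names two time-to-event analyses against historical registry controls: "A Kaplan-Meier analysis will compare changes in conjugated/direct bilirubin concentration over time between groups", and "Cox proportional hazard models will be used to estimate crude and adjusted hazard ratios". It gives no censoring time, proportionality check, time-varying effect or list of adjustment variables.

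Section XIII also bases the sample size on about 50% of treated patients and 10% of controls resolving within 8 weeks. Section IV ties the end of treatment to each patient's progress, so treated follow-up is open-ended. The follow-up of registry controls is not stated. The only fixed times given for between-group comparisons are 8 weeks (sample size) and 14 weeks (secondary endpoints).

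**The concern.** A Cox model with one treatment term assumes that the ratio of the two event rates is the same throughout follow-up. The course in section X is a delayed effect: nothing beyond background resolution at first, then a concentrated run of normalizations. Under such a course the fitted ratio is a weighted average of an early ratio near 1 and a much larger later one, and the weights depend on how long the groups are observed.

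The hazard ratio is the only effect size that section XIII names for the time-to-event comparison. With open-ended follow-up on one side and unstated follow-up on the other, the reported value could be moved several-fold by a cut-off chosen after the data are in. The controls are historical, so no design feature makes follow-up equal.

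**Working it through.** **The plan's own figure.** For 10% against 50%, two-sided alpha 0.05, power 0.80 and mean proportion 0.30:

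n = [1.96·√(2·0.30·0.70) + 0.842·√(0.10·0.90 + 0.50·0.50)]² / 0.40² = (1.270 + 0.491)² / 0.16 ≈ 19.4, so 20 per group.

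This is within one patient of the stated 19, at which power is about 0.79. The calculation compares two proportions at 8 weeks and does not use a hazard ratio.

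**Earliest drug-related event under section X.** Entry requires "Patients who have a conjugated or direct bilirubin of ≥ 3 mg/dl for more than 4 weeks" (section IX, Inclusion Criteria) and the event is a value below 1 mg/dl. Predicted time = 8 + (baseline − 1)/1 weeks. At the entry minimum this is 8 + 2 = 10 weeks; at 7 mg/dl it is 8 + 6 = 14 weeks, which matches the worked example.

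**The course implied by section XIII.** With constant hazards, 50% and 10% at 8 weeks give a ratio of ln(0.5)/ln(0.9) = 0.693/0.105 ≈ 6.6 at any cut-off. A lag in which levels stay at pre-treatment values cannot produce 50% resolution by week 8 in patients who start at 3 mg/dl or more, so the two sections conflict.

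**Cox ratio under section X, by common cut-off.**

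- From the plan: lag 8 weeks, fall 1 mg/dl per week, control rate 10% per 8 weeks. Taken as constant, the control hazard is −ln(0.9)/8 ≈ 0.0132 per week.
- Assumed, not in the documents: baseline uniform 3 to 11 mg/dl; SD 2 weeks around the predicted time; 60, 80 or 100% responders; the control hazard acting as background in treated patients too.
- A responder's time is the earlier of the predicted time and a background time. Non-responders and controls have the background time only.

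| Responders | 8 weeks | 14 weeks | 20 weeks | 52 weeks |
|---|---|---|---|---|
| 60% | 1.1 | 2.8 | 4.0 | 2.6 |
| 80% | 1.2 | 3.5 | 6.0 | 3.9 |
| 100% | 1.2 | 4.0 | 9.8 | 10.4 |

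These are simulated values. A run with 200,000 per group agrees with the first two rows to within about 0.1 and puts the last at 1.2, 4.3, 10.6 and 11.5. The upper ends are therefore good to about 10%.

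**Unequal follow-up.** With 80% responders, following treated patients for 52 weeks but controls for 8 weeks gives 1.1. With controls followed for 14 weeks it gives 3.5. Once one group has left the risk set, later events in the other add nothing, so the group with the shorter follow-up sets the ratio.

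**Baseline mix.** At a fixed 14 weeks, with all treated patients responding, background in both groups and no spread in the lag, the ratio is 16.8 for baseline 3 to 7 mg/dl, 3.8 for 3 to 12 and 2.3 for 3 to 20.

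**The case against.** The strongest objection is that the plan does not commit itself to a lag. Section XIII's sample-size assumption is a large early effect, which a constant ratio would fit. A reader might infer that the plan's expected course rules out a Cox model; the documents do not support that, because they hold two incompatible courses. The objection stands as far as that inference goes. It does not remove the problem, since nothing in the plan protects the estimate if section X is the correct description.

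A reader might also infer that the ratio averages opposite effects, with apparent early harm. Ratios well below 1 at 8 weeks (0.12 to 0.16 with 60 to 80% responders) do appear if treated patients are denied any background resolution. Section X describes no early change, not harm, and with the same background in both groups the early ratio is close to 1.

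Nor do the documents show that the ratio depends mainly on the cut-off. If everyone responds it levels off once all have normalized, from about week 26 in the table's last row, and the baseline mix matters at least as much at 14 weeks. The later decline needs non-responders, whose share is assumed.

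Finally, 8 weeks is not a planned end of follow-up, and every cut-off of 14 weeks or later in the table favours treatment. Cox is neither the basis of the sample size nor named as the primary test, and section XIII also lists tests of proportions and Kaplan-Meier curves. All of this is correct and limits the consequence. Without a fixed horizon for the primary endpoint, however, those analyses do not supply a defined effect size in its place.

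**Conclusion.** The point holds in a conditional form. If bilirubin follows the course in section X, hazards are not proportional and the planned ratio is not a single quantity: it rises from about 1 at 8 weeks to roughly 3 to 4 at 14 weeks, the two times that the plan names. From 20 to 52 weeks it either levels off near 10 or 11 or falls back, depending on how many patients respond. If instead the sample-size assumption holds with constant hazards, a ratio of about 6.6 would be stable.

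The direction of the result at realistic follow-up is not in doubt under these assumptions; the size of the reported effect is. The exact values rest on the assumed baseline range, spread, responder share and constant background rate. The non-proportionality itself needs only the lag in section X and the control rate in section XIII. The sample size and the conduct of the study are not affected by this point. It should be corrected before analysis.

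**What to change.** 1. Reconcile the time courses in sections X and XIII, and state which one the analysis assumes.
2. Set one follow-up horizon, beyond the 8-week lag and common to treated patients and registry controls. Under section X a patient starting at 11 mg/dl is predicted to normalize at 8 + 10 = 18 weeks, so the expected baseline range should inform the choice.
3. Make the effect measure the between-group difference in Kaplan-Meier cumulative normalization at that horizon. The difference in restricted mean time to normalization up to the same horizon can be added. These measures also vary with the horizon, but it is then fixed in advance and the same for both groups.
4. If Cox is kept for adjustment, which is reasonable with non-randomized controls, censor both groups at the same horizon, include baseline bilirubin and pre-specify a proportional-hazards check. Where proportionality fails, report period-specific effects instead of one overall ratio.

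The cost is analysis-plan wording and a few lines of code, with no change to patients, visits or treatment. The horizon must be one that registry follow-up can support. The loss is a single familiar summary ratio.
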